## 7. DISCONTINUATION/WITHDRAWAL CRITERIA

### 7.1. Discontinuation of Study Drug

Subjects who wish to stop treatment for any reason may stop at any time during the study. If the study treatment is permanently discontinued, the subject will remain in the study to complete all assessments as described in the SoA ([Table 1](#) and Table 2) through Study Week 8 (end-of-treatment visit). Subjects should also be encouraged to return for a final follow-up visit 4 weeks after the Study Week 8 visit for Part 1 and 2 weeks after the Study Week 8 visit for Part 2, at which the end-of-study assessments will be performed.

Details regarding subjects who discontinue study drug before Study Week 12 in Part 1 or Study Week 10 in Part 2 will be recorded on the appropriate page(s) of the eCRF. If a subject discontinues study drug because of an AE, the investigator may be requested to schedule follow-up visits until the event has resolved or stabilized ([Section 8.3.3](#)).

Reasons for discontinuing study drug may include:

- Use of prohibited/excluded medications (see [Section 6.7.1](#))
- Administrative decision by the investigator or the sponsor
- Subject noncompliance with the study drug dosing schedule ([Section 6.4](#))
- Development of an AE ([Section 8.3](#))
- Unblinding of subject's study drug treatment assignment ([Section 6.3](#))
- Subject becomes pregnant ([Section 8.3.5](#))
- Other

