### **9.3.2. Efficacy Analyses**

The FAS will be used for the efficacy analyses. In general, descriptive statistics for continuous variables will consist of subject count, mean, standard deviation, median, and range (min, max). Descriptive statistics for categorical variables will consist of subject counts and percentages. The primary estimand is designed to answer the research question on the treatment effect of investigational therapy versus placebo in addition to standard of care on the change in office-measured blood pressure from baseline to Study Week 8. Details of the estimand components are provided in the SAP.

The primary efficacy endpoint is the Study Week 8 change from baseline in SBP. The primary efficacy analysis will be performed using a mixed model repeated measures approach with fixed effects of categorical terms for treatment, week, and treatment by week interaction and baseline SBP as a fixed continuous covariate. A least square estimate, along with the 90% CI, of the mean difference between each dose group and the placebo group will be provided for each time point, with the primary analysis inference based on the evaluation of the Week 8 estimates. P-values corresponding to the pairwise tests, not adjusted for multiplicity, of the difference between each dose group versus placebo will be provided only for the Study Week 8 time point.

For the office-measured secondary efficacy endpoints, a similar approach will be used as for the primary estimand analysis. Both primary and secondary SBP and DBP endpoints will be summarized descriptively by study week. The ABPM parameters (SBP and DBP) will also be summarized descriptively by study week.

A response to treatment assessment will be based upon whether or not the office-measured BP achieved values of  $\leq 130/80$  mmHg by the end of Study Week 8. Subjects without an assessment at Study Week 8 or who have received rescue medications will be considered as failures. The proportion of successes will be calculated for each treatment group. The timing of the first value of  $\leq 130/80$  mmHg will be summarized using a Kaplan-Meier approach within treatment group, and the relationship to baseline SBP and DBP will also be explored.

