5.4 Withdrawals, Dropouts, Loss to Follow-up

Subjects who withdraw from treatment will still be followed until End of Study, unless they withdraw from study also. Withdrawals will not be replaced.

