5.5 Visit Windows

No analysis visit windowing will be performed for this study with the exception of early termination visits (specifically the End of Treatment visit, which is recorded on the eCRF as Week 8/EOT). Early termination assessments will be re-numbered to an analysis visit based on their windowed visits defined by actual study day (see table below).

For the supplemental Estimand (defined in Section 6.4.1.5) only, post-treatment visits will also be re-numbered based on their windowed visits defined by actual study day. Specially, this refers to the End of Study visit at Week 12 (Part 1) or Week 10 (Part 2). This is because the supplemental

Estimand uses all observed data, regardless of whether they are on treatment or not. As the supplemental Estimand is only defined for SBP, this is the only variable for which the EOS visit windowing needs to be applied.

The following analysis visit windows will apply to early termination visits:

| Visit | Target Study Day | Analysis Window |
|--------------------|--------------------|--|
| Baseline | Day 1 | ≤ Day of first dose in Double-blind treatment period |
| Week 1 – Visit 7 | Day 7 (± 2) | Day 2 – Day 10 |
| Week 2 – Visit 8 | Day 14 (± 2) | Day 11 – Day 17 |
| Week 3 – Visit 9 | Day 21 (± 2) | Day 18 – Day 24 |
| Week 4 – Visit 10 | Day 28 (± 2) | Day 25 – Day 31 |
| Week 5 – Visit 11 | Day 35 (± 2) | Day 32 – Day 38 |
| Week 6 – Visit 12 | Day 42 (± 2) | Day 39 – Day 45 |
| Week 7 – Visit 13 | Day 49 (± 2) | Day 46 – Day 52 |
| Week 8 – Visit 14 | Day 56 (± 2) | ≥ Day 53 |
| Week 9 – Visit 15 | 3 days post EOS | N/A |
| Week 12 – Visit 16 | Day 84 (± 2) | N/A |

If more than one assessment occurs within a single visit window, the analysis will take the nominal visit assessment if there is a nominal visit or the later assessment if there is no nominal visit assessment.

For by-visit summaries, endpoints will be analyzed according to the nominal visits (i.e. assigned visit). Unscheduled measurements will not be included in by-visit summaries but will contribute to the Baseline timepoint and/or minimum/maximum/worst value (e.g. shift table), if applicable.

Listings will include all visit data, including unscheduled visits, in chronological order based on visit date.

[figure not shown]

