6.4.2.4 Proportion with BP <130/80 mmHg

Each subject will be assessed as a success if the Week 8 value for SBP is ≤ 130 mm Hg and DBP ≤ 80 mm Hg; a subject will be assessed as a failure otherwise. The number and proportion of subjects will be provided by treatment group.

Number and proportion of subjects who achieve only the SBP or DBP goal (but not both) will be provided as well. Subjects missing an assessment at Week 8 or who have received rescue medications will also be considered as failures.

Relationship between success (as defined above) and SBP levels at baseline (mm Hg) will be evaluated graphically using by-treatment scattered boxplots of baseline SBP with success/failure marked for each subject.

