| | | | Missing data for non-treatment related reasons (e.g. accidental or covid-related Death, or Treatment discontinuation not related to treatment) will be imputed using jump-to-reference method with placebo as reference, where the mean of the placebo group at that visit will be imputed as the missing value, regardless of which treatment group the subject was assigned to. |
| Supplemental Estimand | Supplemental estimator 1 | Patients with uncontrolled hypertension (hypertensive despite receiving \geq 2 antihypertensives) as defined by the inclusion/exclusion criteria in the protocol. | See primary Estimand |
| Supplemental Estimand | Supplemental estimator 2 | Per Protocol Set | See primary Estimand |

| | | | | |
|--------------------------|----------------|----------------------|--|---|
| | | | corresponds to a treatment policy strategy. | regardless of treatment discontinuation or other ICE. Any remaining missing data will be imputed from MMRM model directly, which implicitly assumes missing-at-random (MAR). |
| Key Secondary Estimand 1 | Main estimator | See primary Estimand | Change in 24-hour ABPM parameters (systolic and diastolic) from baseline to the end of Study | ANCOVA with treatment group as a factor and a baseline value as a covariate. Missing ABPM is replaced by repeated test; no other imputation for missing data, regardless of cause. |
| Key Secondary Estimand 2 | Main estimator | See primary Estimand | See primary Estimand | Difference between each active dose and placebo in 24-hour mean, daytime mean, and nighttime mean change from baseline to EOT in ABPM SBP and DBP |
| Key Secondary Estimand 3 | Main estimator | See primary Estimand | See primary Estimand | Difference between each active dose and placebo in mean change from baseline to Study Weeks 1, 2, 3, 4, 5, 6, and 7 in office-measured SBP |

| Key Secondary Estimand 4 | Main estimator | Proportion of subjects who achieve in office-measured BP of \leq 130/80 mm Hg by the end of Study Week 8 | Rescue medication use, Death (non-Covid/non-accidental) or Treatment discontinuation for treatment-related reason (i.e. lack of efficacy, toxicity); treatment failure | Difference between each active dose and placebo in proportion of success. | 7, and 8 in office-measured DBP | |
|--------------------------|----------------|--|--|---|---------------------------------|--|
| | | | | | | |

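### The BP-control endpoint has two scoring rules: a subject who stops drug for a treatment-related reason but is at goal at Week 8 is a success under SAP 6.4.2.4 and a failure under SAP 9.2.

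*SAP*

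**What the plan says.** Three places define who counts as a responder.

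- **SAP 6.4.2.4.** The rule starts from the observed reading: "Each subject will be assessed as a success if the Week 8 value for SBP is ≤ 130 mm Hg", with DBP at or below 80 as well. Two conditions override this to failure: "Subjects missing an assessment at Week 8 or who have received rescue medications will also be considered as failures". Stopping study drug is not mentioned.
- **Protocol 9.3.2.** It has the same two overrides: "Subjects without an assessment at Study Week 8 or who have received rescue medications will be considered as failures". It is also silent on discontinuation.
- **SAP 9.2, Key Secondary Estimand 4.** For the same ≤130/80 proportion, the intercurrent-event strategy reads: "Rescue medication use, Death (non-Covid/non-accidental) or Treatment discontinuation for treatment-related reason (i.e. lack of efficacy, toxicity); treatment failure".

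Two further places bear on whether a subject who stopped drug has a Week 8 BP. Protocol 7.1 states: "If the study treatment is permanently discontinued, the subject will remain in the study to complete all assessments as described in the SoA". SAP 5.4 states: "Subjects who withdraw from treatment will still be followed until End of Study, unless they withdraw from study also".

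No section says which rule governs. SAP section 7, which lists the changes from the protocol, does not mention the difference.

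**The concern.** An estimand table exists to fix how intercurrent events are handled, and the analysis section should carry that out. Here the analysis section leaves out one of the events that the estimand treats as failure. Follow-up continues after drug is stopped, so the omission is not made harmless by missing data: the design deliberately collects BP readings off drug.

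Two programmers working in good faith from different sections of the SAP could report different control rates from the same data. SAP 9.2 defines the summary measure as the active-minus-placebo difference in proportion of success, so the scoring feeds straight into the reported contrast. If the choice were made after unblinding, it would be hard to show that it was independent of the results.

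**Working it through.** **Inputs.** Success and failure rules: SAP 6.4.2.4, SAP 9.2 and Protocol 9.3.2. Follow-up: Protocol 7.1 and SAP 5.4. Visit mapping: SAP 5.5. Definition of rescue: SAP 6.7.6. Planned group sizes: about 30 per arm in Part 1, about 30 active and 6 placebo in Part 2 (Protocol synopsis). The plan states no figure for this endpoint, so there is none to reproduce.

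**Step 1: apply both rules to the same subject.**

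| Subject | SAP 6.4.2.4 | SAP 9.2 |
|---|---|---|
| Stopped for a treatment-related reason, no rescue, Week 8 BP observed at goal | success | failure |
| Same, Week 8 BP above goal | failure | failure |
| Same, Week 8 BP missing | failure | failure |
| Rescue used, Week 8 BP at goal | failure | failure |
| On drug, no rescue, Week 8 BP at goal | success | success |

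Only the first row conflicts. An example is drug stopped at Week 3 for symptomatic hypotension, no rescue, and a Week 8 BP of 126/76.

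**Step 2: can the first row occur?** It needs an observed Week 8 reading off drug. SAP 5.5 says: "Early termination assessments will be re-numbered to an analysis visit based on their windowed visits defined by actual study day". An end-of-treatment visit before Day 53 is therefore assigned to an earlier week. If nothing later is recorded, Week 8 is missing and both rules give failure. A reading exists if the subject attends Week 8 as Protocol 7.1 requires, or if the end-of-treatment visit falls on or after Day 53. SAP 6.7.6 narrows the row further: an antihypertensive started up to the Week 8 office reading counts as rescue even after study drug has stopped, and that is failure under both rules. The conflict is narrow, but the design allows it.

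**Step 3: does the primary estimand settle it?** SAP 6.4.1.1 treats withdrawal for a treatment-related reason (ICE 3) as failure and imputes the baseline value. That rule is written for change in SBP, whereas responder status also needs DBP. SAP 6.4.2.2 and 6.4.2.3 refer back to the primary analysis; 6.4.2.4 does not.

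**Step 4: size per subject.** The change in an arm's proportion is 100 × k/n points, for k subjects in the first row and n in the arm.

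- Part 1 arm, n = 30: k = 1 gives 100 × 1/30 = 3.3; k = 2 gives 6.7; k = 3 gives 10.0.
- Part 2 placebo, n = 6: k = 1 gives 100 × 1/6 = 16.7.

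The documents do not give k; 1 to 3 is an assumed range, used only to show the scale. Going from the 9.2 rule to the 6.4.2.4 rule, the active-minus-placebo difference changes by 100 × (k_active/n_active − k_placebo/n_placebo). In Part 2, one such subject in each group gives 3.3 − 16.7 = −13.3 points (before rounding, 100 × (1/30 − 1/6)). The sign depends on where these subjects fall.

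**The case against.** The strongest reply is that the documents can be read together. Protocol 9.3.2 says that office-measured secondary endpoints follow an approach similar to the primary estimand, and the primary estimand fails treatment-related withdrawals. SAP 6.4.2.4 never says that a subject who stopped drug is a success, so 9.2 could be taken to fill its silence. This does not remove the conflict. Protocol 9.3.2 goes on to give the responder endpoint its own rule with only two overrides, and 6.4.2.4 repeats that rule without referring to 9.2 or to the primary estimand.

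A second reply is that 9.2 is the outlier, because the protocol and 6.4.2.4 agree. That has force. Amending 9.2 would also reconcile the documents, at the price of changing the stated estimand.

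A third is that the extracted 9.2 table is broken. Its method cell for this estimand cannot be read and nothing here rests on it; the strategy cell is legible.

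A reader might also infer that the 6.4.2.4 rule favours MLS-101, by crediting poorly tolerated doses with control reached off drug. The documents do not support that:

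- They give no rate of treatment-related stopping by arm and do not show that most subjects who stop will have a Week 8 BP.
- Entry required an average SBP of at least 130 on background therapy, and nothing indicates that BP stays at goal once drug is stopped.
- Protocol 6.5.2 allows hypotension to be managed without permanent discontinuation.
- A placebo subject in the first row would shift the contrast the other way.

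Nor do the documents name this endpoint as a basis for dose selection; they say only that the study informs it.

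**Conclusion.** The inconsistency is real and confined to one kind of record: treatment-related discontinuation, no rescue, and an observed Week 8 BP at goal. For that record SAP 6.4.2.4 does not estimate Key Secondary Estimand 4 as SAP 9.2 states it. Each such subject is worth 3.3 points in a Part 1 arm of about 30 and 16.7 points in the Part 2 placebo group of about 6. How many there will be, and in which arms, cannot be told from the documents, so no direction or total size of bias is claimed.

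The consequence is limited. SAP 6.4.2 treats the secondary analyses as supportive and any inference as descriptive, and 6.4.2.4 plans only counts and proportions. All Part 2 analyses are exploratory. The primary analysis is unaffected. The conclusion assumes that 6.4.2.4 is applied as written to observed Week 8 readings.

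**What to change.** Before unblinding, use one rule in both places. To match the stated estimand:

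1. In SAP 6.4.2.4, require for success a Week 8 SBP ≤130 and DBP ≤80, no rescue, and no treatment discontinuation for a treatment-related reason.
2. Define that reason by the recorded categories already used for ICE 3 in SAP 6.4.1.1, namely Adverse Event or Physician Decision. The 9.2 wording (lack of efficacy, toxicity) matches none of the discontinuation categories listed in SAP 6.3.1 and so cannot be programmed directly from them; align it.
3. List the departure from Protocol 9.3.2 in SAP section 7.
4. Keep the observed-BP proportion as a supportive row, so that the protocol's version is still reported.

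If the sponsor prefers the observed-BP rule, the strategy cell in 9.2 must be amended instead; the two cannot both stand. SAP 2.4 keeps unblinded sponsor staff out of finalising the SAP, and 2.5.2 keeps the main team blinded until the end of Part 2, so that team can still make the choice blind.

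The cost is a few lines of SAP text, one extra condition in the derivation and one added table row. The downside is that the reported control rate may be slightly lower in any arm with such subjects.

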6.4.2.5 Time to first occurrence of BP <130/80 mmHg

The time to first in-office-measured BP of $\leq 130/80$ mmHg up to Week 8/EOT will be analyzed using the Kaplan-Meier method. For subjects who achieve a BP of $\leq 130/80$ mmHg, time to first BP of $\leq 130/80$ mmHg will be calculated as: date of first in office-measured BP of $\leq 130/80$ mmHg minus date of first dose of randomized study drug plus 1.

Subjects who fail to achieve a BP of $\leq 130/80$ mmHg prior to Week 8/EOT will be censored at the Week 8/EOT and will be calculated as: Week 8/EOT – date of first dose of randomized study drug + 1.

Subjects who are lost to follow-up prior to Week 8/EOT will be censored at the date of the last known BP assessment and will be calculated as: date of last known BP assessment – date of first dose of randomized study drug + 1.

Subjects who took rescue medications will be censored on the date he/she initiated the rescue medication.

A cumulative incidence plot for time from first dose of randomized study drug to BP $\leq 130/80$ will also be provided, with each treatment group represented by a different line.

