6.4.1.1 Primary Estimand

The Primary Estimand is designed to answer the research question on the treatment effect of investigational therapy in addition to standard of care (SOC) vs. placebo in addition to SOC on the change in office blood pressure from baseline to Week 8.

This Estimand is constructed in line with ICH E9 (R1) addendum. The five components that define the Estimand of interest are:

- Treatment is 5 MLS-101 dose levels (12.5 mg BID, 25 mg BID, 12.5 mg QD, 50 mg QD, or 100mg QD) vs placebo, regardless of compliance.
- Population: Patients with uncontrolled hypertension (hypertensive despite receiving ≥ 2 antihypertensives) as defined by the inclusion/exclusion criteria in the protocol.
- Patient-level outcome / variable: Change in office-measured SBP from baseline to Week 8.
- Population-level summary: Mean (SD) change in office SBP from baseline to Week 8.
- Inter-current events:

The following Intercurrent Events (ICE) have been identified which could prevent measurement of the primary outcome or change the interpretation of the measured primary outcome:

1. Initiation of rescue medications
2. Death before the completion of 8 weeks period (except #5)
3. Patient withdrawal from treatment before the completion of 8 weeks period for treatment-related reason or worsening (defined as reason for treatment withdrawal being "Adverse Event" or "Physician Decision").
4. Patient withdrawal from treatment before the completion of 8 weeks period for non-treatment related reason
5. Death due to COVID-19 / Accidental death

Event 1 will be treated as treatment failure. The observed SBP that triggered rescue medication will be imputed.

Events 2 and 3 will be handled as treatment failure. The baseline value will be imputed.

Events 4 and 5 will be handled using a hypothetical strategy assuming that the clinical course for either treatment group follows their own group with the estimate of the endpoint value obtained using MMRM in the primary analysis.

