9.2 Estimands

| Estimand | Estimator | Treatment | Population | Variable | Strategy for Handling ICES | Summary Measure | Method of Estimation |
|------------------|-------------------------|---|--|---|--|---|---|
| Primary Estimand | Main estimator | Comparison between Placebo and 5 MLS-101 dose levels (12.5 mg BID, 25 mg BID, 12.5 mg QD, 50 mg QD, or 100mg QD), regardless of adherence | Patients with uncontrolled hypertension (hypertensive despite receiving ≥ 2 antihypertensives) as defined by the inclusion/exclusion criteria in the protocol. | Change in office-measured SBP (AOBP as recorded in EDC) from baseline to the end of Study Week 8. | Rescue medication use: treatment failure; value prior to rescue carried forward to subsequent visits | Difference between each active dose and placebo in mean change from baseline to Week 8 in office-measured SBP | The primary efficacy analysis will be performed using a mixed model repeated measures (MMRM) approach with fixed effects of categorical terms for treatment, week, and treatment by week interaction, and baseline SBP as a fixed continuous covariate. In this model, the subject is considered as a random effect, where an unstructured variance/covariance matrix is assumed for describing the correlation of repeated measurements over time. |
| | | | | Full Analysis Set | Death (non-Covid/non-accidental) or Treatment discontinuation for treatment-related reason (i.e. lack of efficacy, toxicity); treatment failure; baseline value carried forward to subsequent visits | In case of non-convergence of the model estimates, alternative covariance structures will be considered (in the following order: Toeplitz, AR(1), CS). The first covariance structure that converges will be deemed the main estimator. | Missing data for non-treatment related reasons (e.g. accidental or covid-related Death, or Treatment discontinuation not related to treatment: hypothetical strategy imputed based on MMRM for each treatment group |
| Primary Estimand | Sensitivity estimator 1 | See primary Estimand | See primary Estimand | See primary Estimand | See primary Estimand | See primary Estimand | MMRM with fixed effects of categorical terms for treatment, week, and treatment by week interaction, and baseline SBP as a fixed continuous |

| | | | |
|-----------------------|--------------------------|---|---|
| | | | covariate. Subject is considered as a random effect, with the covariance structure selected for the main estimator. |

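### Time to first BP control censors subjects at rescue although the matching responder endpoint counts rescue as failure, so the curve can overstate the proportion reaching goal without rescue

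*SAP*

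**What the plan says.** SAP 6.4.2.5 analyses time from first randomized dose to the first office BP at or below 130/80 "mmHg up to Week 8/EOT will be analyzed using the Kaplan-Meier method". Its rule for rescue is: "Subjects who took rescue medications will be censored on the date he/she initiated the rescue medication". It adds "A cumulative incidence plot for time from first dose of randomized study drug to BP" at or below 130/80, by treatment group, and names neither an estimator nor a competing event.

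Closely related endpoints handle rescue differently:

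- **Responder endpoint, same threshold (SAP 6.4.2.4):** "Subjects missing an assessment at Week 8 or who have received rescue medications will also be considered as failures".
- **Estimand table row for that proportion (SAP 9.2):** "Rescue medication use, Death (non-Covid/non-accidental) or Treatment discontinuation for treatment-related reason" are grouped together as treatment failure.
- **Primary estimand (SAP 6.4.1.1):** "Event 1 will be treated as treatment failure. The observed SBP that triggered rescue medication will be imputed". The table in SAP 9.2 agrees: "Rescue medication use: treatment failure; value prior to rescue carried forward to subsequent visits".
- **Protocol 9.4:** for office-measured efficacy endpoints, values after rescue are discarded and the last pre-rescue value stands in for them.

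Protocol 9.3.2 asks for a Kaplan-Meier summary of time to control within each treatment group and gives no censoring rule. The SAP gives no reason for censoring at rescue and states no estimand for this curve. SAP section 7 does not mention the choice.

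**The concern.** Kaplan-Meier treats a censored subject as someone who would go on to reach goal at the same rate as those still at risk. A subject censored at rescue hands his or her weight to subjects who did not need rescue. The curve then estimates control in a world without rescue, and it does even that only if rescue is unrelated to prognosis. The primary estimand speaks of the SBP reading that triggered rescue, so a link to uncontrolled BP is likely.

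Under Protocol 9.4, a rescued subject who had not reached goal keeps an uncontrolled value to Week 8. Such a subject should stay in the denominator as a non-event.

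At stake is how the by-arm curves are read. A reader will take their Week 8 height as the percentage who got to goal on the assigned treatment. With about 30 subjects planned per arm in Part 1, a few early rescues can lift that height visibly.

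**Working it through.** **Inputs.** From the documents: weekly visits over Weeks 1 to 8, about 30 subjects per arm in Part 1 (Protocol synopsis), and the censoring rule above. The plan states no figure for this analysis. Its only precision figure concerns mean SBP change and reproduces: 1.645 × 9 × √(2/30) = 3.82, against ±3.8 mmHg. Numbers controlled, numbers rescued and rescue timing are not in the documents, so all of those below are assumptions.

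**Formulas.** With n_k at risk and d_k first-control events at visit k, the plan's curve at Week 8 is 1 − Π(1 − d_k/n_k), where rescued subjects leave n_k. With rescue as failure and no other censoring, the value is the number reaching goal before rescue divided by the number randomized.

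**Step 1: one arm of 30.** Assume 12 first-control events, at Weeks 1 to 8: 1, 2, 2, 2, 2, 1, 1, 1. The rescue-as-failure value is 12/30 = 40.0%. Rescues fall among uncontrolled subjects, in equal numbers just after the Week 2, 3 and 4 visits. Between rescues the Kaplan-Meier factors telescope:

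| Rescued | Survivor product | Plan's curve |
|---|---|---|
| 0 | 18/30 | 40.0% |
| 3 | (27/30)(24/26)(21/23)(15/20) = 0.569 | 43.1% |
| 6 | (27/30)(23/25)(19/21)(12/17) = 0.529 | 47.1% |
| 9 | (27/30)(22/24)(17/19)(9/14) = 0.475 | 52.5% |

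If all rescues come after the last control event, the curve stays at 40.0%.

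**Step 2: timing.** Take 40% controlled, 5% of the arm at each of the eight visits, and spread rescue evenly after the Week 1 to 4 visits or after the Week 5 to 8 visits.

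- 30% rescued early: 1 − (0.95/1)(0.825/0.875)(0.70/0.75)(0.575/0.625)(0.30/0.50) = 53.9%.
- 30% rescued late: 1 − (0.75/1)(0.625/0.675)(0.50/0.55)(0.375/0.425) = 44.3%.
- 10% rescued early: 1 − (0.95/1)(0.875/0.925)(0.80/0.85)(0.725/0.775)(0.50/0.70) = 43.5%.
- 10% rescued late: 1 − (0.75/1)(0.675/0.725)(0.60/0.65)(0.525/0.575) = 41.1%.

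That gives the range of about 41% to 54% where 40% is correct.

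**Step 3: a milder case and the arm contrast.** Let rescue be independent of prognosis, with constant weekly hazards. C is the probability of control by Week 8 absent rescue, and R the probability of rescue absent control. Then h = 1 − (1 − C)^(1/8), r = 1 − (1 − R)^(1/7), q = (1 − h)(1 − r), and the rescue-as-failure incidence is h(1 − q^8)/(1 − q). For C = 40% and R = 20%: h = 0.0619, r = 0.0314, q = 0.9087, incidence 36.3%, where the plan's curve shows 40%. Over C of 30% to 60% and R of 5% to 30%, the overstatement runs from 0.7 to 7.9 points.

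Now let the plan's curves show 50% on active and 30% on placebo, a gap of 20 points:

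- Rescue 5% active, 20% placebo: 48.9 − 27.1 = 21.8 points.
- Rescue 20% active, 5% placebo: 45.5 − 29.3 = 16.2 points.

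So the displayed gap can be too small or too large.

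**The case against.** The best case for leaving the rule alone has four parts.

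1. **Rescue is not failure throughout the SAP.** The supplementary estimand in 6.4.1.5 follows a treatment policy strategy, and the ABPM analysis ignores rescue. This stands. The close conflict is with the responder endpoint at the same threshold. In the primary estimand, failure means carrying a value forward, which is not itself a time-to-event rule.
2. **Rescue need not mean uncontrolled BP.** SAP 6.7.6 derives it as any antihypertensive started in the window, with no BP threshold. Some starts may have other reasons, so informative censoring is likely but not certain for each case. The overstatement relative to rescue-as-failure does not depend on this: Step 3 shows it with rescue independent of prognosis.
3. **Little rests on the curve.** Time to control is not among the secondary endpoints in SAP 3.1.2, no between-arm test is planned for it, and secondary analyses are supportive. In an arm of 30 with 40% controlled, the 90% half-width of a proportion is 1.645 × √(0.4 × 0.6/30) = 14.7 points, wider than most of the shifts shown. This limits the consequence, but the shift is systematic and avoidable.
4. **The rescue burden is visible elsewhere.** SAP 6.7.6 reports time to rescue by arm. That helps a careful reader but does not correct the control curve.

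A reader might also infer that the curve contradicts the responder table and that a fix would make them agree. It would not: 6.4.2.4 scores the Week 8 value and 6.4.2.5 the first value at goal at any visit, so they can differ with no rescue at all. Nor can one infer a bias for or against the drug from higher rescue on placebo, because the documents give no rescue rate in any arm.

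**Conclusion.** The point holds. Censoring at rescue is at odds with how the SAP treats rescue for the same BP threshold, and no estimand is stated that would justify it. The plan's curve can never lie below the rescue-as-failure incidence, and it lies above whenever a control event follows a rescue in the same arm.

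The size is unknown. Under the assumed patterns it runs from under 1 point to about 14 points (40% shown as 54%), and it is zero if no rescue precedes a later control event. The direction of any distortion between arms is not determined. The cumulative incidence plot is affected if it is drawn from the Kaplan-Meier estimate or with rescue censored, which the text implies but does not spell out.

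A reader might go further and question the primary result. The documents do not support that: the primary model, its significance level and the sample size do not use this analysis. It should be corrected as a supportive display.

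**What to change.** Replace the rescue sentence in SAP 6.4.2.5 with one of two rules:

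- treat rescue before first control as a competing event (failure), and draw Aalen-Johansen cumulative incidence curves by arm; or
- keep rescued subjects who have not reached goal in the risk set as non-events to Week 8/EOT.

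The two coincide only when there is no other censoring. SAP 6.4.2.5 also censors subjects lost to follow-up, so the SAP should name one rule as the main analysis.

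Also state that control reached before rescue counts as an event, since the present sentence, read literally, censors those subjects too. Name the estimator for the cumulative incidence plot. Label the curve as first reaching goal before rescue, with a note that it will not equal the Week 8 responder proportion. If a picture of control absent rescue is wanted, keep the rescue-censored curve as a sensitivity analysis labelled as such.

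The cost is a few sentences in the SAP, a small programming change and slightly lower displayed control rates.
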